5.1.3 Pilot study

The interventions in phase 2 are expected to increase attendance amongst those who have not attended for 10% to 20% (see above). In proof of concept studies a larger significance level and increased power is appropriate so that potential beneficial treatments are not rejected.[15] With 120 subjects in each arm, the study will have a power of 90% to reject the null hypothesis of no increase in uptake with a one-sided significance level of 25%.

5.2 Statistical analysis

A detailed statistical analysis plan will be prepared and agreed with the Trial Steering Committee (TSC) at the end of the pilot study. Due to the nature of the primary outcome we envisage complete data being available on all subjects in the trial regarding attendance, via the Exeter system.

Descriptive analysis will tabulate the rate of attendance and rate differences by intervention group. Formal inferential statistical analysis of cluster randomised trials needs to take account of the clustering of patients within practices.[16] This will be accomplished by fitting a logistic multilevel

model,[17] with covariates for treatment group, the uptake rate for each practices in the year prior to the study, and site (Manchester/Salford and Trafford/Aberdeen) with a random effect included for practice. Where new practices have formed or practices have merged, the baseline uptake rate will be imputed. Preliminary analyses will also include a site with treatment interaction to investigate possible differential effects of an intervention between Aberdeen and NW, important for understanding the implications of vaccination. A sub-group analysis of just the Aberdeen cohort will examine the effect of pre-study vaccination status on uptake and any interaction with the interventions. In stage 1 of the study the effect of a pre-leaflet and on-line booking on uptake are being tested within a factorial design in Manchester PCT. Whilst we do not envisage an interaction between the two analyses a sub-analysis in the Manchester cohort will test for an interaction between the interventions.

For the nurse-navigator intervention statistical analysis will be based on intention-to-treat (ITT). In addition the proportion contacting the nurse navigator and the proportions subsequently attending will be estimated. Similarly for on-line booking ITT will be used. Analysis will also estimate the proportion of women who use the on-line booking system and the proportion of those who subsequently attend.

Due to differences in the participants and context there may be differences in the intervention and the treatment effect between sites (England and Scotland). For example, the pre-leaflet intervention will differ between the Manchester/Salford/Trafford and Aberdeen sites due to the vaccination and younger age of the Aberdeen cohort. Data analysis for the pre-leaflet will therefore be carried out separately for each cohort. For other interventions (HPV self sampling, nurse navigator and timed appointments) that are being tested across sites, differences in the intervention will be not so great. For these a treatment-site interaction will be used to investigate site difference. The number of practices allocated to different interventions across the sites should ensure a demographic spread which will reduce the risk of confounding.

6. Economic Analysis and Organisational Impact Assessment

An economic analysis will be conducted alongside this project. The analysis has been designed as a “streamlined” study along similar lines to the statistical analysis, and will make extensive use of routine screening data. The economic analysis will have three components:

- 1) The costs of each intervention will be calculated. For the leaflet, this will include development costs and printing and distribution costs. For internet booking the costs will include programming and IT changes required to implement the system. For the specialist nurse navigator, the calculated costs will include all letters, telephone calls and publicity

material, and average time involved in providing advice and facilitating access, which will be obtained from a simple log maintained by navigators over sample periods.

- 2) Other health care costs related to the interventions will be calculated. These will include attendances at screening clinics, consultations, and screening-related tests and diagnostic procedures. These will also be captured using routine information sources as described above.
- 3) Cost-effectiveness will be calculated. This will take two forms: One, the incremental cost per percentage point increase in screening attendance within the study time-horizon will be estimated for each of the strategies being examined compared to standard practice. Second, lifetime cost-effectiveness and cost-utility will be estimated. Construction of a new lifetime model is not proposed, as several validated models already exist and have been used to produce published estimates of the cost-effectiveness of the current screening programme. Instead, we propose to combine the cost and attendance results of the study with these published estimates of the lifetime costs and effects of participating in cervical cancer screening programmes, to obtain lifetime cost-effectiveness and cost-utility estimates. Results will be presented within a probabilistic framework, using cost-effectiveness acceptability curves and net-benefit statistics.

This approach will provide reliable estimates of cost and cost-effectiveness while adhering to the general approach of the project, which maximises use of routine data sources and minimises the need for direct contact with women participating in the study. The health economist would also be involved in the design and analysis of a discrete choice experiment (DCE). In 2013/2014, a sample of approximately 2000 non-responders to screening will be identified by the screening agency. These women will be invited to state their preferences for different attributes of the possible interventions, in order to assist the selection and detailed design of interventions for the main trial phase. Non-responding women in Aberdeen will be included to measure the effect of HPV vaccination in women's preferences. It is not envisaged that the results of the DCE would be used directly in the final economic evaluation, although it will be possible to compare stated preferences with revealed preferences manifested in uptake rates, and may also be possible to give estimates of values placed on attributes other than clinical effectiveness, such as convenience, control and confidentiality.

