3.7 Randomisation methods

The screening uptake rate in the target age group, the uptake rate after a reminder and the screening uptake rate overall in the year prior to the study are likely to be strong predictors of the trial outcome measures. Data for the year prior to the trial will be extracted from the Exeter system to estimate these rates for each practice. These rates will then be used to balance the characteristics of treatment groups. To do this, the procedure described by Butler and Raab [11] will be adapted for the complex factorial design of this trial. Where practices have formed or merged the baseline uptake rates required for the minimization will be imputed using characteristics of the practice such as size and location or data from the constituent practices. A sample of allocations that give good balance between the 4 intervention factors will be identified using stochastic methods. An allocation will then be randomly selected from the sample of good allocations. This procedure will be stratified by PCT and carried out with the names and location of the practices concealed.

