Self test kits will be sent by the trial centre. About 600 self test kits will be sent out. So that the acceptability of the two kit can be compared, women will be randomised to receive either kit types using randomisation stratified by site with a random block size of 4,6 or 8. In each study site the screening centre will assign kits in order according to a pre-prepared list.

Figure 2 Phase 2

	Pre Leaflet	Online Booking	Self Test Sent	Self Test Offered	Nurse Nav	Nurse Nav + Offered	Timed appointment	Control	Total
Manchester	Yes	Yes	3	4	3	4	2	8	24
	Yes	No	3	3	4	3	2	9	24
	No	Yes	4	3	3	3	3	9	25
	No	No	2	3	2	3	4	10	24
Salford &	Yes	-	6	5	6	6	5	16	44
Trafford	No	-	4	5	4	4	5	17	39
Aberdeen	Yes	-	4	5	6	3	5	15	38
	No	-	5	6	5	5	6	13	40
Total			31	34	33	31	32	97	258

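### The 5.2 model leaves out variables used to balance the randomisation in 3.7 (it uses one unnamed uptake rate of three and merges Salford with Trafford), so its tests are somewhat conservative.

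*Protocol*

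**What the plan says.** Protocol 3.7 starts from three practice-level rates, all taken from the year before the trial: "The screening uptake rate in the target age group, the uptake rate after a reminder and the screening uptake rate overall". It describes them as "likely to be strong predictors of the trial outcome measures" and says: "These rates will then be used to balance the characteristics of treatment groups". On strata it says: "This procedure will be stratified by PCT and carried out with the names and location of the practices concealed". The same section looks for allocations that balance across four intervention factors, so phase 1 and phase 2 are allocated jointly.

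Protocol 5.2 sets a logistic multilevel model with a random practice effect, a treatment-group term and two adjustments: "the uptake rate for each practices in the year prior to the study, and site (Manchester/Salford and Trafford/Aberdeen"). The rate is singular and is not identified. The site term has three levels.

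In 5.1, Figure 1 shows Salford (26 leaflet, 21 control) and Trafford (18 and 18) as separate rows. Figure 2 shows them as one block and crosses the phase 2 arms with leaflet and online booking.

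**The concern.** An analysis should normally reflect the restrictions placed on the randomisation. Balancing on a predictor removes its contribution from the true variance of the treatment estimate. If the model then omits that predictor, its between-practice variance goes into the practice random effect. The reported standard error is too wide, the type I error falls below nominal, and precision gained at allocation is not used.

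The after-a-reminder rate is a plausible candidate to matter in phase 2, which enrols women who have not attended after a reminder. Because the rate in 5.2 is not named, the choice of covariate in the primary model also stays open.

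A second, smaller question is whether the phase 2 models include the phase 1 allocation, since Figure 2 is only approximately balanced on it.

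**Working it through.** **1. The two sections side by side.**

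| | 3.7 (allocation) | 5.2 (model) |
|---|---|---|
| Uptake rates | three, each named | one, not identified |
| Geography | PCT | Manchester / Salford with Trafford / Aberdeen |
| Other factor or phase | balanced jointly over four factors | not listed; may or may not sit in the treatment-group term |

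**2. The plan's own power.** Design effect DE = 1 + (m - 1) x ICC; effective n = practices x m / DE; two-proportion normal approximation, with 5% two-sided assumed.
- Leaflet (5.1.1: 92 v 88 practices, m = 40, ICC 0.026, +5 points; 30% control uptake taken from the stated upper limit): DE = 1 + 39 x 0.026 = 2.014; effective n = 3680/2.014 = 1827 and 3520/2.014 = 1748; power 89.1% (stated 89%).
- Online booking (49 v 48, 30% v 37.5%): 93.6% (stated 93%).
- Phase 2 (5.1.2: 30 v 100 practices, m = 20, ICC 0.07, 10% v 20%, alpha 0.05/5 = 0.01): DE = 1 + 19 x 0.07 = 2.33; power 93.1% (stated above 80%, which also allows for varying cluster size).

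The stated powers therefore use the unadjusted ICC and claim no gain from covariates.

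**3. What extra covariates could add.** With R2 the share of between-practice variance that the added terms remove, DE = (1 - ICC) + m x ICC x (1 - R2). The documents give no R2, so this is a range.

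| Extra R2 | 0 | 0.1 | 0.2 | 0.3 | 0.5 |
|---|---|---|---|---|---|
| Leaflet power, % | 89.1 | 90.6 | 92.1 | 93.5 | 96.0 |
| Online booking, % | 93.6 | 94.7 | 95.7 | 96.7 | 98.2 |
| Phase 2, % | 93.1 | 94.5 | 95.8 | 96.9 | 98.6 |

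This is not the cost of the 5.2 model. The balanced allocation already delivers part of the gain, and one rate is already in the model. That cost needs simulation.

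**4. Simulated restricted allocation, leaflet comparison.** Assumptions: three equally weighted rates with pairwise correlation rho, together explaining 50% or 80% of between-practice variance; allocation balanced on all three within PCT. Practice-level regression, 4,000 runs per scenario. Planned = one rate and merged site; full = three rates and separate PCTs.

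| rho, R2 | Planned SE / true SE (no effect) | Type I error, planned | Power, planned v full |
|---|---|---|---|
| 0.3, 0.8 | 0.0137/0.0118 = 1.16 | 2.5% | 97.5% v 98.8% |
| 0.5, 0.8 | 0.0133/0.0118 = 1.13 | 2.4% | 97.7% v 98.7% |
| 0.5, 0.5 | 0.0142/0.0132 = 1.08 | 3.6% | 95.0% v 95.4% |
| 0.8, 0.8 | 0.0125/0.0118 = 1.06 | 4.0% | 98.2% v 98.5% |
| 0.8, 0.5 | 0.0137/0.0133 = 1.03 | 4.1% | 95.9% v 95.8% |

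The ratios use rounded values; the range is about 3-17%.

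**5. Logistic random-intercept model.** Phase 1 (700 runs): power, planned v full, was 96.1% v 98.4% (rho 0.3, R2 0.8), 93.1% v 94.3% (0.5, 0.5) and 94.6% v 94.9% (0.8, 0.5). Phase 2, one arm against control at 10% v 20%, with rho and R2 both 0.5 (600 runs): 94.3% v 96.8%; type I error 0.5% v 1.0% at nominal 1%.

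Three cautions apply:
- In phase 2, 0.5% of 600 runs is 3 rejections.
- In phase 2 with an effect present, the full model's SE (0.178) was below its empirical value (0.193), so the 2.5-point gap is if anything generous.
- The logistic runs built in no uptake difference between Salford and Trafford, so they do not measure the cost of merging them.

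**6. Cross-phase balance in Figure 2.** Leaflet practices by arm: self-test sent 16/31, offered 17/34, nurse navigator 19/33, navigator or self-test 16/31, timed appointments 14/32, control 48/97 (49.5%). The plan compares each arm with control. The largest gaps are 57.6 - 49.5 = +8.1 points (nurse navigator) and 43.8 - 49.5 = -5.7 points (timed appointments). If a 5-point leaflet effect carried over in full, the shifts would be 0.081 x 5 = 0.40 and 0.057 x 5 = 0.29 points, against a planned difference of 10.

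**The case against.** The strongest reply is that 5.2 defers detail to a statistical analysis plan that is not shown, where the full covariate list may be settled; that the error is conservative; and that the power promised in 5.1 never depended on adjustment. The last two stand. The first stands in part: the later plan may well resolve this, but 5.2 does set the covariates itself, and that list does not match 3.7.

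The three rates also overlap, since the target age group is part of the overall figure. If they are highly correlated, one of them does nearly all the work. Figure 2 and 3.6 treat Salford and Trafford together, and no figure in the protocol suggests that their uptake differs. The treatment-group term may be meant to cover both phases, and the planned leaflet-by-booking interaction test in Manchester needs both factors in that model. These points make parts of the list unclear; they do not remove the mismatch.

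Two stronger readings are tempting:
- **A large power loss.** A simulation with a 7-point phase 2 effect, and an omitted rate explaining 30-50% of between-practice variance, gives power of 76.8% v 83.5% and 75.6% v 86.0%. The protocol plans phase 2 on 10% v 20%, gives ICC 0.07 as a ceiling, and supports no such R2.
- **A leaflet effect leaking into phase 2.** Nurse navigator (58% leaflet) against timed appointments (44%) looks uneven, but that is not a planned comparison. Against control the shifts are those in step 6 of the working, and they are chance imbalance.

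**Conclusion.** The mismatch is real. Section 5.2 adjusts for one unidentified rate where 3.7 balanced on three, and merges two PCTs that 3.7 treats as strata. The direction is settled: standard errors somewhat too large and tests conservative.

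The size cannot be derived from the documents. With rates correlated 0.3 to 0.8 and explaining 50-80% of between-practice variance, the phase 1 standard error is about 3-17% too large, and power is about 0-2.5 points below the full model across the phase 1 and phase 2 runs. The power loss is near zero at correlation 0.8. The separate cost of merging Salford with Trafford is not quantified.

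A reader might infer that the trial falls short of its stated power, or that results are tilted towards the interventions. Neither follows: the stated powers rest on the unadjusted ICC and the planned model does not fall below them, and a conservative test does not favour the interventions. The cross-phase terms improve precision and clarity; they do not correct a material bias. This is an inexpensive improvement to the primary model and no threat to the trial's validity.

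**What to change.** In 5.2, list as covariates:
- all three prior-year rates named in 3.7;
- the strata as randomised: Manchester, Salford, Trafford, Aberdeen;
- in phase 2 models, the leaflet and online-booking allocation;
- in the Manchester phase 1 models, each of leaflet and online booking in the other's model.

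If a single rate is preferred, name it before outcome data are seen and justify dropping the other two. If phase 2 was in fact stratified with Salford and Trafford combined, as Figure 2 may imply, say so in 3.7 and match the phase 2 model to it.

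The cost is wording only. The rates and allocations are already held for the randomisation. Relative to 5.2 as written, a phase 2 model gains at most five parameters (two rates, one site level, two phase 1 factors), which 258 practices support easily.

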6.1 Qualitative interviews (pilot phase)

6.1.1 Aims

1. To investigate the acceptability of three novel interventions designed to improve young women's receptivity to, and uptake of, cervical screening programmes.
2. To identify the attributes and their levels for the discrete choice experiment (DCE) exploring young women's preferences for cervical screening programmes.

6.1.2 *Methods*

This is a telephone interview based qualitative study with young women.

6.1.3 *Participants and recruitment*

A sub sample of 21 to 33 women who are taking part in the pilot study in Manchester (in phase 1) will be recruited to this qualitative component. In order to capture a diverse range of views, purposive sampling will ensure we include a mix of women who are offered the three novel interventions (nurse navigator, self-sampling, timed appointments). We will also attempt to interview a mix of white British and non-white British women, and interview women who have taken up the offer of the intervention and those who have declined. The final number of interviews will be determined when saturation is achieved. Our previous experience suggests this sample size will allow inclusion of participants with a breadth of experiences while retaining a depth to each interview. All the women who are invited to take part in the pilot study will also receive a participant information sheet and consent form for this qualitative component of the study (see Appendix 2). The details of the women who agree to take part in the pilot study *and* to be interviewed (name, allocated arm in pilot study, phone number and best times to telephone) will be forwarded from the lead researcher in Manchester to the qualitative researcher in York. This will be done using a nominated fax, with a telephone call to pre-warn of transmission. Alternatively, the women can send a reply slip with a FREEPOST envelope directly to the University of York.

The screening agency, in conjunction with the researchers in Manchester, will be able to identify women who do not respond to the invitation to participate in the pilot study. A different participant information sheet (see Appendix 3), consent form with attached reply slip and a FREEPOST envelope will be sent to these women from the screening agency, avoiding the need to pass patient identifiable data onto the research team. Women will be asked to return the reply slip and consent form directly to the qualitative researcher in York who will then be able to arrange an interview.

Women will then be telephoned by a researcher from York to conduct the interview. Before the interview starts the researcher will revisit the purpose and format of the interview with the participant, discuss any questions she may have, and reconfirm that she is happy to be interviewed, and for the interview to be recorded.

6.1.4 *Data Collection*

The telephone interviews will be semi-structured, with the use of a topic guide to ensure that the same general issues are discussed in each interview. However, there will be scope for participants to raise issues that are important to them and we will adopt an iterative approach where data collection and data analysis occur simultaneously. This will allow us to develop the topic guide to explore emerging

issues and to probe, and eventually confirm, the importance of different attributes of cervical screening programmes for the DCE. Whilst there are two sets of questions to meet the two aims of the interviews (see Appendix 4) these are not mutually exclusive. Women's views on a novel intervention may usefully inform the identification of the attributes for the DCE.

Both sets of initial questions are informed by existing literature on women's views of cervical screening programmes [18-21] and good practice for identifying attributes and levels for a discrete choice experiment [22].

Where consent is given, interviews will be digitally recorded. Where consent is not provided by the participant, the researcher will take detailed notes.

6.1.5 Data Analysis

The audio-recordings will be transcribed verbatim with all personal data anonymised to ensure confidentiality. The data will be analysed using the constant comparison method through thematic coding of the data [23]. Coding will take place using a combination of a prior themes and emergent themes. Negative cases will actively be sought throughout the analysis and emerging ideas and themes modified in response [24]. ATLAS-ti software will aid data handling.

6.2 Discrete choice experiment (DCE)

6.2.1 Aims

To investigate the value non-responding women place on cervical screening and the three novel interventions designed to improve young women's uptake at first invitation.

6.2.2 Methods

This is a postal/online survey questionnaire DCE. The DCE questionnaire will comprise a section on women's general views about the value of the current cervical screening programme and a second section containing a number of choice scenarios which incorporate the attributes and levels developed from the qualitative data collected for the three novel interventions. The questionnaire will also include questions on basic demographic information such as age, education and employment status. Women will also be asked about any difficulties encountered when completing the DCE questionnaire.

6.2.3 Participants and recruitment

A sample of 2000 Manchester non-responders to cervical screening invitation separate to those invited into pilot interventions or into phase I will be recruited for the DCE. This figure is informed by work conducted by the ISPOR Conjoint Analysis Experimental Design Task Force in which simulation studies were used to explore the impact of alternative sample sizes on the precision of

parameter estimates. [Reed et al (2012) Constructing Experimental Designs for Discrete-Choice Experiments: Report of Value in Health. In press]. The screening agency, in conjunction with the researchers in Manchester, will identify non-responding women who are eligible to participate in the DCE study. Women will be sent a participant information sheet the paper-based version of the DCE and a FREEPOST envelope by the screening agency. As women will have the choice of whether to complete the paper-based version or to complete the DCE online (see section 6.24) the weblink for the online version will be provided in the patient information sheet. The paper-based DCE will be returned to York in the freepost envelope.

